#### 6.6.2.1.8 Osteonecrosis

Osteonecrosis has been reported in subjects treated with cabozantinib. Additional risk factors include use of bisphosphonates and denosumab, chemotherapy and anti-angiogenic drugs, use of corticosteroids, local radiotherapy, and dental or orofacial surgery procedures.

Osteonecrosis of the jaw (ONJ) can manifest as jaw pain, osteomyelitis, osteitis, bone erosion, tooth or periodontal infection, toothache, gingival ulceration, or gingival erosion. Persistent pain or slow healing of the mouth or jaw after dental surgery may also be manifestations of osteonecrosis.

Advise subjects regarding oral hygiene practice and to quickly report symptoms to investigator. Caution should be used in subjects receiving bisphosphonates.

CONFIDENTIAL

Protocol XL184-313 Protocol Amendment 3.0  
Page 97 of 193

Invasive dental procedures should be avoided. In cases where dental procedures are unavoidable, treatment with cabozantinib should be interrupted for at least 4 weeks prior to the procedure and resumed after complete wound healing has occurred. Bone healing may often require a protracted time.

#### **6.6.2.1.9 Proteinuria**

Proteinuria has been reported with cabozantinib. Proteinuria should be monitored by measuring UPCR. [Table 6-9](#) provides treatment guidelines for proteinuria deemed related to cabozantinib.

Cabozantinib should be discontinued in subjects who develop nephrotic syndrome (proteinuria > 3.5 grams per day in combination with low blood protein levels, high cholesterol levels, high triglyceride levels, and edema).

CONFIDENTIAL

Protocol XL184-313 Protocol Amendment 3.0  
Page 98 of 193

**Table 6-9: Management of Proteinuria Associated with Cabozantinib**

Severity of Proteinuria (UPCR)	Management of Proteinuria
$\leq 1 \text{ mg/mg}$ ( $\leq 113.1 \text{ mg/mmol}$ )	

• No change in cabozantinib treatment or monitoring

$> 1 \text{ and } < 3.5 \text{ mg/mg}$ ( $> 226.2 \text{ and } < 395.9 \text{ mg/mmol}$ )	

• Consider confirming with a 24-h protein assessment within 7 days

• No change in cabozantinib treatment required if UPCR <math>\leq 2 \text{ mg/mg}</math> or urine protein <math>\leq 2 \text{ g/24 h}</math> on 24-h urine collection.

• Dose reduce or interrupt cabozantinib treatment if UPCR <math>> 2 \text{ mg/mg}</math> on repeat UPCR testing or urine protein <math>> 2 \text{ g/24 h}</math> on 24-h urine collection. Continue cabozantinib on a reduced dose if UPCR decreases to <math>< 2 \text{ mg/mg}</math>. Consider interrupting cabozantinib treatment if UPCR remains <math>> 2 \text{ mg/mg}</math> despite a dose reduction until UPCR decreases to <math>< 2 \text{ mg/mg}</math>. Restart cabozantinib treatment at a reduced dose after a dose interruption unless otherwise approved by the Sponsor.

• If UPCR <math>> 2 \text{ mg/mg}</math>, repeat UPCR monitoring within 7 days and once per week. If UPCR <math>< 2 \text{ mg/mg}</math> on 2 consecutive readings, UPCR monitoring can revert to protocol-specific times. (Second reading is confirmatory and can be done within 1 week of first reading.)

$\geq 3.5 \text{ mg/mg}$ ( $\geq 395.9 \text{ mg/mmol}$ )	

• Interrupt cabozantinib treatment pending repeat UPCR monitoring within 7 days and/or 24-h urine protein.

• If <math>\geq 3.5 \text{ mg/mg}</math> on repeat UPCR monitoring, continue to interrupt cabozantinib treatment and check UPCR every 7 days. If UPCR decreases to <math>< 2 \text{ mg/mg}</math>, restart cabozantinib treatment at a reduced dose and monitoring of UPCR until it remains <math>< 2 \text{ mg/mg}</math> on two consecutive measurements. If UPCR monitoring is determined to be stable (<math>< 20\%</math> change) for 1 month then continue with UPCR monitoring per protocol or as clinically indicated.

Nephrotic syndrome	

• Discontinue cabozantinib treatment

UPCR, urine protein/creatinine ratio.

#### 6.6.2.1.10 Nervous System Disorders

Cabozantinib appears to represent minimal risk of adverse neurological effects based on nonclinical Good Laboratory Practice (GLP)-compliant toxicology studies. Dysphonia, dysgeusia, headache, dizziness, confusional state, convulsion, depression, memory impairment, hypoesthesia, peripheral neuropathy, insomnia, ataxia, and encephalopathy have been observed in clinical studies with cabozantinib. The development of any new or progressive, unexplained neurological symptoms should be assessed for underlying causes.

CONFIDENTIAL

RPLS has been reported. RPLS should be considered in any subject presenting with seizures, headache, visual disturbances, confusion or altered mental function. Cabozantinib treatment should be discontinued in subjects with RPLS.

#### **6.6.2.1.11 Infections and Infestations**

Infections are commonly observed in cancer subjects. Predisposing risk factors include decreased immune status (eg, after myelosuppressive anti-cancer therapies, splenectomy), destructive growth of the underlying malignancy including bone marrow infiltration with suppression of normal hematopoiesis, as well as the presence of IV devices.

Infections and abscesses should be treated with appropriate local care and systemic therapy. Cabozantinib should be interrupted until adequate healing has taken place.

#### **6.6.2.1.12 Blood and Lymphatic System Disorders**

Hematological toxicities (ie, neutropenia and thrombocytopenia) and associated complications have been observed after administration of cabozantinib and may be managed with dose interruptions and/or dose reductions. Subjects with hematologic toxicities may require additional or more frequent laboratory tests according to institutional guidelines.

Dose reductions or dose interruptions for hematological toxicities are not mandated but can be applied as clinically indicated. Supportive care for thrombocytopenia or anemia, such as transfusions, may be managed according to institutional guidelines. The use of colony-stimulating growth factors should be considered. Febrile neutropenia or evidence of infection associated with neutropenia must be assessed immediately and treated appropriately and in a timely manner according to institutional guidelines.

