## 6.6.2 Management of AEs Associated with Cabozantinib/Placebo

Throughout the remainder of [Section 6](#) the term “cabozantinib” refers to blinded oral study treatment of cabozantinib or cabozantinib-matched placebo. Considerations for management of AEs associated with oral study medication are presented below.

- The assigned dose for cabozantinib is 40 mg qd.
- Two dose reduction levels of cabozantinib (20 mg qd and 20 mg every other day [qod]) are permitted (see [Table 6-4](#)).

CONFIDENTIAL

Protocol XL184-313 Protocol Amendment 3.0  
Page 88 of 193

- Dose modification criteria for treatment-related AEs of cabozantinib are shown in [Table 6-5](#). Grade 1 and tolerable Grade 2 AEs are managed similarly; Grade 3 and intolerable Grade 2 AEs are managed similarly.
- Dose reinstitution and reescalation after dose interruptions and/or reductions:
  - If the subject recovers from his or her toxicities to CTCAE v5  $\leq$  Grade 1 or to the baseline value (or lower) and the AE was unrelated to oral study medication, then oral study medication may be restarted with no change in dose.
  - If the subject recovers from his or her toxicities to  $\leq$  Grade 1 or to the baseline value (or lower) and the AE was deemed related to oral study medication, then cabozantinib may be reinitiated but this must be at a reduced dose (see [Table 6-4](#)).
  - Subjects receiving a dose of 20 mg every other day (qod) may be restarted at the same dose if deemed safe at the discretion of the Investigator. Subjects unable to tolerate a dose of 20 mg qod must discontinue cabozantinib/placebo upon discussion with the Sponsor.
  - Re-escalation to the previous dose may be allowed at the discretion of the Investigator but no sooner than 10 days beyond improvement of AEs that led to the dose reduction to Grade 1 (or baseline value), as long as AEs are deemed tolerable and easily managed by optimized supportive treatment. Dose reescalation is not allowed following a cabozantinib-related dose reduction for Grade 4 hematologic toxicities or Grade 4 AEs affecting major organs (eg, central nervous system [CNS], cardiac, hepatic, renal, pulmonary GI).

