**Table 6-5: Dose Modifications for Cabozantinib-Related AEs**

CTCAE v5 Grade	Recommended Guidelines for Management
Grade 1 AEs	Add supportive care as indicated. Continue cabozantinib at the current dose level if AE is manageable and tolerable.
Grade 2 AEs that are tolerable and are easily managed	Continue cabozantinib at the current dose level with supportive care.
Grade 2 AEs that are intolerable and cannot be adequately managed	Cabozantinib should be dose reduced or interrupted. Note: It is recommended that dose interruptions be as brief as possible.
Grade 3 AEs (except clinically non-relevant laboratory abnormalities)	Cabozantinib should be interrupted unless the toxicity can be easily managed with a dose reduction of cabozantinib and optimal medical care. Note: It is recommended that dose interruptions be as brief as possible.
Grade 4 AEs (except clinically non-relevant laboratory abnormalities)	Cabozantinib must be interrupted immediately. In general, cabozantinib should be discontinued unless the following criteria are met: 

• Subject is deriving clear clinical benefit as determined by the Investigator and agreed by the Sponsor

• Toxicity can be managed with a dose reduction of cabozantinib following recovery to Grade 1 (or baseline value) and optimal medical care

 Sponsor must be contacted to discuss treatment continuation upon resolution of AEs.

AE, adverse event.

Note: Cabozantinib dose modification criteria for specific medical conditions are provided in [Section 6.6.2.1](#).

CONFIDENTIAL

Protocol XL184-313 Protocol Amendment 3.0  
Page 90 of 193

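### For clinically relevant, cabozantinib-related Grade 4 neutropenia or thrombocytopenia, Protocol Table 6-5 requires interruption while Section 6.6.2.1.12 leaves it to judgment, and nothing says which governs

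*Protocol*

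**What the plan says.** Protocol Section 6.6.2 presents Table 6-5 as the source of dose modification criteria for adverse events related to cabozantinib (the term covers the blinded oral drug in both arms). It states no hematologic exemption. The Grade 4 row of the table covers "Grade 4 AEs (except clinically non-relevant laboratory abnormalities"), and its instruction reads "Cabozantinib must be interrupted immediately. In general, cabozantinib should be discontinued unless the following criteria are met". The criteria that follow concern clear clinical benefit and whether the toxicity can be managed at a reduced dose after recovery. The row also requires contact with the sponsor about continuing.

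Section 6.6.2.1.12 deals with hematological toxicities, which it specifies as neutropenia and thrombocytopenia, and their complications. It says they "may be managed with dose interruptions and/or dose reductions", and then: "Dose reductions or dose interruptions for hematological toxicities are not mandated but can be applied as clinically indicated". It mentions no grade and does not refer to Table 6-5.

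Two pointers connect the texts. The note under Table 6-5 says "Cabozantinib dose modification criteria for specific medical conditions are provided in" Section 6.6.2.1. The last bullet of Section 6.6.2 lists the adverse events for which Section 6.6.2.1 gives guidelines, and blood system disorders are on that list.

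**The concern.** A rule on stopping drug for a Grade 4 event should have one reading. Here an investigator who starts from the table finds an obligation, and one who starts from the blood-disorder subsection finds discretion.

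More than the hold itself depends on the answer. Under Table 6-5, interruption at Grade 4 brings discontinuation as the default and a discussion with the sponsor before treatment continues. Section 6.6.2 adds that oral drug restarted after recovery from a related event must be at a reduced dose, apart from subjects already at the lowest level. Section 6.6.2.1.12 triggers none of these steps unless the investigator chooses to act.

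Three things are at stake: consistent handling of a safety event across roughly 180 sites; whether continued dosing counts as a deviation under Protocol Section 5.8; and the SAP summaries of dose intensity, holds and modifications due to adverse events (SAP Sections 6.5.2, 6.6.2 and 6.6.3), which would partly reflect which passage a site followed.

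**Working it through.** No arithmetic applies, and the plan gives no figure to reproduce. The check is to set the texts side by side and go through the cases.

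| Source | Scope | Is interruption required? |
|---|---|---|
| Table 6-5, Grade 4 row | Cabozantinib-related Grade 4 events, except laboratory findings without clinical relevance | Yes, at once; discontinuation is the usual outcome |
| Section 6.6.2.1.12 | Neutropenia and thrombocytopenia, any grade | No; allowed when clinically indicated |
| Table 6-5 note and last bullet of Section 6.6.2 | Specific conditions, including blood disorders | Point to Section 6.6.2.1; silent on precedence |

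1. **Grade 4 cytopenia not related to cabozantinib.** Table 6-5 does not apply, so there is no conflict.
2. **Related Grade 4 cytopenia judged to be a laboratory finding without clinical relevance.** The row's exception removes it from the table, so there is no conflict.
3. **Related and clinically relevant Grade 4 neutropenia or thrombocytopenia.** The row applies and so does Section 6.6.2.1.12. The first obliges interruption; the second says there is no such obligation.
4. **Can both texts be satisfied?** Yes, if the drug is interrupted, because Section 6.6.2.1.12 permits interruption. If the drug is continued, only Section 6.6.2.1.12 is satisfied. The texts therefore disagree on whether the step is compulsory.
5. **Does any text settle case 3?** The two pointers say where specific guidance is found, not that it replaces the table. The subsections do not all stand apart from the table either: Section 6.6.2.1.16 on electrolyte disorders sends the reader back to Table 6-5, while Section 6.6.2.1.12 does not mention it.
6. **Is the table merely advisory?** Its column is headed "Recommended Guidelines for Management". Within the column, though, the Grade 4 row says *must*, whereas the Grade 3 row and the row for intolerable Grade 2 events say *should*. The heading does not remove that distinction.

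How often case 3 would arise is not given. Section 6.6.2.1 lists thrombocytopenia, neutropenia and leukopenia among laboratory-related events seen in at least 5% of cabozantinib-treated subjects, without grade. In the Phase 1 triplet data (Section 1.6, 29 subjects), the listed Grade 3 or 4 laboratory abnormalities include one case of decreased platelets and no neutropenia. In the triplet arm of the Phase 3 trial that compared cabozantinib plus nivolumab with sunitinib (44 treated subjects), one thrombocytopenia is listed among the serious events, again without grade.

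**The case against.** The strongest reply is that the specific rule governs the general one. Two pointers lead from the general text to Section 6.6.2.1, and one of them names blood disorders. An experienced investigator could reasonably conclude that Section 6.6.2.1.12 is the operative rule. That reading is natural and may be what was intended. It remains an inference: no sentence states it, and the electrolyte subsection shows that at least one specific subsection defers to the table.

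The second reply is that the laboratory exception disposes of most cytopenias. It does remove some. It cannot remove all, because Section 6.6.2.1.12 also covers associated complications, including febrile neutropenia.

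The third reply is that Section 6.6 lets investigators interrupt at any time. That is true, but it concerns what is permitted; the open question is what is required.

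Three stronger readings are tempting, and the documents do not support them:

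- A reader might infer that the two texts give opposite orders. They do not, since interruption complies with both.
- A reader might cite the re-escalation rule in Section 6.6.2, "Dose reescalation is not allowed following a cabozantinib-related dose reduction for Grade 4 hematologic toxicities", as a further contradiction. It governs what follows once a reduction has been made and does not require one, so it is compatible with discretion.
- A reader might see a mirror-image conflict for infections, because Section 6.6.2.1.11 says "Cabozantinib should be interrupted until adequate healing has taken place" while Table 6-5 continues drug for Grade 1 and tolerable Grade 2 events. That depends on reading Section 6.6.2.1.11 as covering trivial infections related to cabozantinib. The subsection speaks of infections and abscesses needing local care and systemic therapy, and attributes risk largely to the cancer, immune status and intravenous devices.

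**Conclusion.** The point holds in a narrow form. For a clinically relevant, cabozantinib-related Grade 4 neutropenia or thrombocytopenia, the protocol leaves unclear whether interruption of the oral drug is obligatory, and two sites could act differently while each cites its text. This rests on the wording alone and on the absence of any statement of precedence.

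Its size cannot be derived from the documents and may be small. A reader might multiply the 5% threshold by the 420 subjects per arm to get 21 (0.05 × 420), but that threshold refers to events of any grade in a general cabozantinib list, not to clinically relevant Grade 4 events in this trial. A reader might also infer that the ambiguity falls mainly on the experimental arm. The documents give no by-arm data, and Table 6-10 addresses drug-related thrombocytopenia, neutropenia and leukopenia for nivolumab and ipilimumab, which both arms receive.

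The matter is a cross-reference inconsistency in safety text, worth correcting because it bears on subject management and costs little to correct. No effect on the primary PFS analysis is claimed.

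**What to change.** Reconcile Section 6.6.2.1.12 with the Grade 4 row of Table 6-5, and state which of the two governs and at which grades. Carry the same statement into Section 6.6.2 and the note under Table 6-5, so that a reader reaches the same answer from either starting point. The clinical team decides which instruction stands; this review takes no position on that.

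The cost is a protocol clarification or an administrative letter to sites. No new procedures, assessments or data collection are needed, and the SAP does not change.

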#### **6.6.2.1.13 Fatigue**

Common causes of fatigue, such as anemia, deconditioning, emotional distress (depression and/or anxiety), poor nutrition, dehydration, sleep disturbance, and hypothyroidism should be ruled out and treated according to standard of care. Pharmacological management should be considered after disease-specific morbidities have been excluded when not prohibited.

#### **6.6.2.1.14 Weight Loss**

Anorexia and weight loss should be managed according to local standard of care including nutritional support. Pharmacologic therapy should be considered for appetite enhancement when not prohibited by a particular protocol.

#### **6.6.2.1.15 Corrected QT Prolongation**

The effect of orally administered cabozantinib 140 mg qd on QTc interval was evaluated in a placebo-controlled study in subjects with MTC. A mean increase in QTcF of 10-15 ms was observed after 4 weeks after initiating cabozantinib treatment. A concentration-QTc relationship could not be definitively established. Changes in cardiac wave form morphology or new rhythms were not observed. No cabozantinib-treated subjects in this study had a QTcF > 500 ms. Review of the larger safety database (~5000 subjects exposed to cabozantinib in clinical trials and in post-marketing experience) confirmed the absence of safety concerns associated with QT prolongation. There were no events of torsades de pointes reported.

Concomitant treatment with strong cytochrome P450 (CYP) 3A4 inhibitors, which may increase cabozantinib plasma concentrations, should be avoided.

If at any time on study there is an increase in QTcF to an absolute value > 500 ms or an increase of > 60 ms above baseline per the site's ECG read, two additional ECGs must be performed with intervals not less than 3 min apart within 30 min after the initial ECG.

If the average QTcF from the three ECGs is > 500 ms or the average increase is > 60 ms above baseline, the following actions must be taken:

- Interrupt cabozantinib treatment
- Immediately notify the Sponsor
- Hospitalize symptomatic subjects (eg, with palpitations, dizziness, syncope, orthostatic hypotension), or those with a significant ventricular arrhythmia on ECG for a thorough cardiology evaluation and management
- Consider cardiology consultation for asymptomatic subjects for evaluation and management
- Check electrolytes, especially magnesium, potassium and calcium; correct abnormalities as clinically indicated
- Check concomitant medications for any medication that may have contributed to QT prolongation, and if possible, discontinue these medications (<http://www.qtdrugs.org>)
- Send ECGs to central ECG laboratory for independent read
- Repeat ECG triplicates hourly until the average QTcF is  $\leq$  500 ms and the average increase is  $\leq$  60 ms above baseline, or a consulting cardiologist or appropriate expert determines that the frequency of ECGs may revert to the schedule in the protocol.

Subjects with QTc prolongation and symptoms must be monitored closely until the QTc elevation and symptoms have resolved. Cabozantinib treatment may be restarted but only at a reduced dose level if all of the following conditions are met:

CONFIDENTIAL

Protocol XL184-313 Protocol Amendment 3.0  
Page 101 of 193

- Symptoms are determined to be unrelated to the QT interval prolongation
- The QTcF value  $> 500$  ms or increase of  $> 60$  ms above baseline is not confirmed by a **cardiologist consultation**.
- Cabozantinib treatment has been interrupted through a minimum of 1 week following the return of the QTcF to  $\leq 500$  ms and  $\leq 60$  ms above baseline
- Sponsor has reviewed all available information and has agreed to the continuation of study treatment.

Following reinitiation of study treatment, ECGs must be repeated weekly for 2 weeks, then every 2 weeks for 1 month, then according to the protocol-defined time points.

Cabozantinib treatment must be permanently discontinued if either of the following applies:

- Cardiac evaluation confirms that symptoms are the consequence of QT interval prolongation
- Recurrence of QTcF prolongation (confirmed by central ECG lab) after reinitiation of study treatment at a reduced dose

#### **6.6.2.1.16 Electrolyte Disorders**

Serum electrolyte disorders including hyponatremia, hypokalemia, hypomagnesemia, and hypophosphatemia have been reported during treatment with cabozantinib, and serum electrolyte levels should be monitored frequently while receiving cabozantinib. Clinically relevant electrolyte disorders should be managed according to the dose modification guidelines as outlined in [Table 6-5](#) or as clinically indicated. Standard clinical practice guidelines should be used for management of electrolyte disorders and may include oral or IV replacement.

#### **6.6.2.1.17 Endocrine Disorders**

Treatment-emergent elevation of thyroid-stimulating hormone (TSH) has been observed with cabozantinib treatment. Currently available data are insufficient to determine the mechanism of thyroid function test alterations and its clinical relevance. Management of thyroid dysfunction (eg, symptomatic hypothyroidism) should follow accepted clinical practice guidelines.

